## **6. Study Objectives and Endpoints**

### ***6.1. Primary Objective***

The primary objective of this study is to evaluate the effectiveness of Spinal Cord Stimulation (SCS) with multiple modalities as compared to conventional SCS in patients with chronic pain when using the Boston Scientific Spectra WaveWriter SCS System.

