### 7.2. Treatment Assignment

All enrolled subjects who pass eligibility criteria will receive a trial. Subjects with a positive trial will proceed to receive permanent implant. Following permanent implant, all subjects' device will be randomized in a 1:1 ratio to either receive:

- WaveWriter Settings – Perception and/or sub-perception programming with all available modalities
- Conventional Settings – Perception programming (up to 1.2 kHz)

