### 7.3. Justification for the Study Design

The study is a prospective, multi-center, parallel group randomized controlled trial with an adaptive design. The study is designed to demonstrate the value of multiple modalities and combining mechanisms for sustained clinically significant pain relief in patients with chronic pain when using the Boston Scientific Spectra WaveWriter SCS System. Additionally, the impact of the Spectra WaveWriter SCS System on global patient outcomes, quality of life and patient preference will also be evaluated.

A prospective study design will eliminate the bias associated with case selection in a retrospective review and will ensure that identical procedures are followed for data capture and review.

A multi-center design will minimize the impact on treatment outcome that may potentially result from differences in patient selection, regional differences in the patient demographic, and differences in investigator technique and patient management.

The study design includes two groups (arms) – WaveWriter group and Conventional group. The WaveWriter group will receive all the programming capabilities available in the WaveWriter SCS System while the conventional group will have limited programming capabilities. The Conventional group will serve as a control in this study. Randomization (1:1) will minimize selection bias and impact of demographic variables.

The primary endpoint is the proportion of subjects with 50% or greater reduction (responder rate) from the Baseline Visit in average overall pain intensity at 3 months post-randomization, with no increase in baseline average daily opioid medications used to treat pain. A 3-month endpoint was chosen as 3 months provides adequate time for a subject to have their programming parameters optimized.

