**10.15. *Unscheduled Visit***

Subjects may have as many unscheduled visits as required for device-related in-office or procedure visits (e.g., optimization of programming during the programming period) or for evaluation of possible adverse events and if applicable, re-positioning, replacement or explant of a device component. Unscheduled visit information will be captured, as applicable.

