#### 11.1.1.1. Hypotheses

The primary statistical hypothesis in this study is that the proportion of subjects with 50% or greater reduction from Baseline Visit in average daily overall pain intensity at 3 months post randomization in the WaveWriter group is non-inferior compared to the Control (i.e. Conventional) group

$$H_0: \pi_t - \pi_c \leq -0.20$$

$$H_1: \pi_t - \pi_c > -0.20$$

Where  $\pi_t$  and  $\pi_c$  are the proportion of subjects with 50% or greater reduction from Baseline in average daily overall pain intensity at 3 months post randomization with no increase in baseline average daily opioid pain medications using Spectra WaveWriter all modalities and conventional settings, respectively. The study's non-inferiority margin is 0.20.

[REDACTED]

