11.1.1.3. Statistical Methods

The 95% confidence interval of  $\pi_t - \pi_c$  will be computed. The study will be considered a success if, using the Intent-To-Treat (ITT) analysis, the lower bound of the two-sided 95% confidence interval for the difference is great than -0.20.

[REDACTED]

[REDACTED]

[REDACTED]

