**11.2. General Statistical Methods**

**11.2.1. Analysis Sets**

- **Intent-to-Treat (ITT) Population:** All subjects who are randomized regardless of the treatment received.
- **Per Protocol (PP) Population:** All subjects who receive the study device, with no major protocol deviations.
- **Safety Population:** All subjects who sign the IRB-approved written Informed Consent form

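### Does the non-inferiority rule lose its meaning because a WaveWriter subject may be programmed with perception stimulation only?

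*Combined protocol and SAP*

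**What the plan says.** Section 7.2 assigns subjects 1:1 to WaveWriter settings, "Perception and/or sub-perception programming with all available modalities", or to conventional settings, given as "Perception programming (up to 1.2 kHz" in a parenthesis. Section 7.3 describes the same contrast as one of capability: "The WaveWriter group will receive all the programming capabilities available in the WaveWriter SCS System while the conventional group will have limited programming capabilities".

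The objective in section 6.1 is "to evaluate the effectiveness of Spinal Cord Stimulation (SCS) with multiple modalities as compared to conventional SCS". Section 11.1.1.1 states the hypothesis by group, with a margin of 0.20, and describes the two proportions as those "using Spectra WaveWriter all modalities and conventional settings, respectively". Section 11.1.1.3 then calls the trial a success if, in the ITT analysis, "the lower bound of the two-sided 95% confidence interval for the difference is great than -0.20".

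Section 11.2.1 defines ITT as everyone randomized, whatever treatment was received, and the per-protocol set as "All subjects who receive the study device, with no major protocol deviations". Both arms receive the same implanted system (section 7).

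Section 10.15 permits unscheduled visits for "optimization of programming during the programming period". Section 10.10 fixes the programs at the Programming Lock Visit, except to resolve a device- or stimulation-related adverse event.

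**The concern.** The words and/or in section 7.2 make perception-only stimulation a permitted state of the WaveWriter arm, and no visible passage requires any minimum use of the other modalities. Sections 6.1 and 11.1.1.1 can be read as being about use of multiple modalities; sections 7.2 and 7.3 read as being about access to them.

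The difference matters more in a non-inferiority trial than in a superiority trial. A WaveWriter subject who ends up on control-type programming moves the observed difference toward 0. Under superiority that is conservative; under this rule it helps the trial succeed. The usual check is the per-protocol analysis, but the definition shown does not screen on modality use, and programming that section 7.2 permits is not on its face a deviation.

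At stake is the inference normally drawn from non-inferiority, that the new treatment itself works about as well as the old. If many WaveWriter subjects were on perception-only programs, the trial could succeed even though the extra modalities did nothing, or did harm in those who used them.

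**Working it through.** **Inputs.** From the documents: margin 0.20, two-sided 95% interval, 1:1 allocation, ITT (sections 7.2, 11.1.1.1, 11.1.1.3). The visible text gives no sample size, response rate or interval method, so there is no figure of the plan's own to reproduce. Assumed: 50, 75, 100 or 150 subjects per arm; control response 70%; an unpooled Wald interval; a share f of the WaveWriter arm on perception-only programs, from 0 to 100%.

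**Step 1: what overlap does to the difference.** Suppose perception-only subjects respond at the control rate and multi-modality users respond d lower. Then

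π_t − π_c = −(1 − f)·d.

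For this to reach −0.20, users must do worse than control by 0.20/(1 − f): 0.20 at f = 0, 0.267 at 25%, 0.40 at 50% and 0.80 at 75%. At f = 100% the difference is 0 for any d.

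**Step 2: how often the rule succeeds.** Take d = 0.20, so that users respond at 50%. Summing exact binomial probabilities over all outcomes whose lower bound exceeds −0.20 gives:

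| f | True difference | n=50 | n=75 | n=100 | n=150 |
|---|---|---|---|---|---|
| 0 | −0.20 | 0.025 | 0.026 | 0.024 | 0.024 |
| 25% | −0.15 | 0.074 | 0.094 | 0.108 | 0.141 |
| 50% | −0.10 | 0.181 | 0.251 | 0.316 | 0.443 |
| 75% | −0.05 | 0.360 | 0.501 | 0.623 | 0.795 |
| 100% | 0 | 0.590 | 0.763 | 0.873 | 0.966 |

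**Step 3: are these errors?** The null hypothesis is π_t − π_c ≤ −0.20. Only the first row lies in it, and there the rate is about 2.5%, as intended. In every other row the alternative is true, so declaring success is correct for the stated hypothesis. The last row is ordinary power with equal arms. The entries become errors only if the hypothesis is replaced by one about users alone.

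**Step 4: would a use-based rule do better?** One candidate keeps every randomized subject. Set U = 1 if a WaveWriter subject's locked programs contain anything the control arm cannot have, and require the lower bound of mean(Y + 0.20·U) in WaveWriter minus mean(Y) in control to exceed 0, where Y is response (0/1).

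- If every WaveWriter subject has one such program, used or not, then U = 1 throughout, mean(Y + 0.20·U) = mean(Y) + 0.20, and the rule is identical to the one in section 11.1.1.3.
- With f = 50%, users at 50%, and U = 0 subjects at exactly the control rate of 70%, simulation gives a false-positive rate of about 2.5%. If assignment itself raised response in U = 0 subjects to 80%, the expected contrast would be 0.5×0.50 + 0.5×0.80 + 0.20×0.5 − 0.70 = +0.05 instead of 0. The false-positive rate would be about 8%, 12% and 16% at 50, 100 and 150 per arm. At 75% it would be about 5%, 6% and 7%.
- With all rates at 70% and f = 50%, power is 0.196, 0.267, 0.335 and 0.467 at 50, 75, 100 and 150 per arm, against 0.590 to 0.966 for the plan's rule.

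**Step 5: is the information lost?** Table 10.1-1 lists programming parameters at the Programming Lock and 3-Month Visits (when programming is performed), and section 12.1.2 has device files uploaded to the data capture system. What was programmed by arm can largely be tabulated from data already planned.

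**The case for a change.** The strongest case for a change is that sections 7.2 and 7.3 and sections 6.1 and 11.1.1.1 can be read as asking two different questions, and the plan does not say which one the success rule answers. Non-inferiority leaves that ambiguity unprotected: overlap helps, and the per-protocol set as shown does not remove it. The use-based bound in step 4 excludes nobody. Its error rate stays at 2.4% to 2.6% even when perception-only subjects differ in prognosis (response of 90% or 50%), provided assignment does not alter their response. The data item would cost little.

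The textual part stands. Perception-only programming is admitted, no minimum-use rule is visible, and a non-inferiority result would not by itself show that the extra modalities work about as well as conventional stimulation.

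The rest is weaker:

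- To say that such a subject is treated exactly like a control is an inference. Section 7.2 adds that all modalities are available, and most of the Randomization Visit text (section 10.9) is redacted, so a minimum-use rule cannot be excluded.
- To say that the per-protocol set cannot remove these subjects goes too far, because a major deviation is not defined in the visible text.
- The proviso on the alternative bound is doubtful. WaveWriter subjects may have tried other modalities before the lock, and no masking is described in the visible text. The bound also scores what a program contains, not what the subject used.

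**Conclusion.** No change follows. Section 7.3 and the group wording of the hypothesis support a comparison of strategies: access to all modalities against conventional programming, analysed by assignment. For that comparison a WaveWriter subject who does best on perception stimulation belongs in the WaveWriter proportion, and the rule has an error rate of about 2.5% on the boundary. The larger figures, 7% to 14% at f = 25% and 18% to 44% at f = 50%, are correct rejections of the stated null hypothesis.

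A non-inferiority finding should be read as a statement about access. An analyst would describe it that way and tabulate the programmed modalities by arm from the planned data. Aligning the wording of sections 7.2 and 11.1.1.1 would record that reading but would alter neither the analysis nor its result. A use-based decision rule is at best a debatable trade: it adds an untestable assumption and, at f = 50%, cuts power to between 20% and 47%.

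This rests on assumed sample sizes and response rates, a Wald interval, and an unknown f that may be 0. It covers only the main protocol, which applies to subjects enrolled under Versions A to C; Appendix A, which governs new subjects, is not visible.

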### 4.2. *Spinal Cord Stimulation*

SCS is effective for chronic intractable pain associated with a variety of conditions, including, but not limited to, FBSS ((Carter et al., 2004, Taylor et al., 2004), complex regional pain syndrome (Sears et al., 2011), and low back pain and leg pain (Cameron et al., 2004). Spinal cord stimulation (SCS) is a less invasive treatment option for FBSS but has generally been reserved for patients who have failed multiple, and indeed all possible, repeat operations. With SCS, an implanted pulse generator (IPG) delivers electrical current to electrode(s) implanted in the epidural space. This current stimulates nerves and can be programmed to direct stimulation to the nerves innervating the painful location, resulting in a reduction of the intensity of that pain (Kumar et al., 2006). Before an SCS system is implanted, a patient often undergoes a screening trial with an electrode that is connected to an external stimulator that the patient wears outside of the body. The results of the screening trial can predict the patient's outcome with an implanted system (Kumar et al., 2006).

In SCS pain relief is realized when the nerves that innervate the painful region(s) are electrically stimulated (North et al., 1990). To increase the chance of success, the electrode contacts are programmed based on the patient feedback to various combinations of contact polarities (anodes and cathodes), pulse rate (or frequency), pulse amplitude (or current), and pulse width.

Traditionally, Spinal Cord Stimulation (SCS) has relied on the understanding that to achieve pain relief, dorsal column stimulation-induced paresthesia has to be generated around the area of pain in order to successfully treat pain (North et al. 1991). However, recent studies indicate that effective pain relief may be obtained by employing stimulation without paresthesia (Van Buyten et al., 2012, De Ridder et al., 2010, Kapural et al 2015).

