**7. Study Design**

The study is a prospective, multi-center, parallel group randomized controlled trial with an adaptive design. All participants will receive the Spectra WaveWriter Spinal Cord Stimulator (SCS) system and followed per the study schedule as shown in study schematic Figure 8.1-1.

[REDACTED]

Figure 7.1-1: COMBO Study Design

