**Table 10.1-1: Data Collection Schedule**

	Screening	Opioid Medication Lock Visit	Baseline Period	Baseline Visit	Implant Procedures (Trial and Permanent)	Randomization/ Activation Visit	Programming Lock Visit	3-Month Visit	6-Month Visit	9-Month Visit	1-Year Visit	2-Year Visit End of Study	Unscheduled Visit
		Up to 35 days following informed consent	14 days post-Medication Lock	(0 - 7 days post Baseline Period)	Up to 90 days post-Baseline Visit	Day 0	70 - 14 days	90 + 14 days post randomization	180 ± 30 days post randomization	270 ± 30 days post randomization	365 ± 30 days post randomization	730 ± 30 days post randomization	
Informed Consent (ICF)	X												
Inclusion/Exclusion Criteria Evaluation	—————→												
Demography				X									
Medical History				X									
Beck Depression Inventory (BDI-II)				X			X				X	X	
Oswestry Disability Index (ODI v2.1a)				X			X	X	X	X	X	X	
Short Form Health Survey 36 Item (SF-36v2)				X			X	X	X	X	X	X	
EQ-5D-5L				X			X	X	X	X	X	X	
Pain Intensity (NRS)				X			X	X	X	X	X	X	
Pain Intensity (VRS)				X			X	X	X	X	X	X	
Pittsburgh Sleep Quality Index (PSQI)				X			X	X	X	X	X	X	
Procedure Information					X †								X **
End of Trial Assessment					X								
Programming Parameters ***					X	X	X	X	X	X	X	X	X
Clinician Global Impression of Change (CGI-C)							X	X	X	X	X	X	
Patient Global Impression of Change (PGI-C)							X	X	X	X	X	X	
Percent Pain Relief (PPR)							X	X	X	X	X	X	
Preference Questionnaire								X	X	X	X	X	
Treatment Satisfaction Questionnaire (TSQM 9m)								X	X	X	X	X	
Concomitant Medications (opioid pain medications)		X		X	X	X	X	X	X	X	X	X	X
Adverse Events (AE)	X	X	X	X	X	X	X	X	X	X	X	X	X

Healing Period (0-28 days)

←————— Opioid Medications Locked —————→

\*\* For unscheduled visits where procedures are performed  
\*\*\* Only when device programming is performed  
† The device will remain off after permanent implant until the Activation Visit

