**10.7. Implant Procedures (Up to 90 days following the Baseline Visit)**

Subjects will have up to 90 days following the Baseline Visit to receive their Spectra WaveWriter System. Subjects will undergo a trial procedure per standard of care. Following a successful trial, i.e. at least 50% pain reduction in their overall pain as compared with Baseline, the subject will proceed to permanent implantation. Subjects with an unsuccessful

implant procedure will be followed for 2 weeks for procedure related adverse events then withdrawn from the study. Acute opioid pain medications may be taken.

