**11.2.8. Multivariable Analyses**

Analysis of covariance will be performed to assess the effects of possible covariates on primary endpoint and some secondary endpoints as necessary. [REDACTED]

[REDACTED]

[REDACTED]

[REDACTED]

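### Should the primary non-inferiority interval have been adjusted for baseline covariates?

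*Combined protocol and SAP*

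**What the plan says.** Section 11.1.1.3 computes a 95% confidence interval for the difference in responder proportions, WaveWriter minus conventional. The study succeeds if, in the ITT analysis, "the lower bound of the two-sided 95% confidence interval for the difference is great than -0.20". No covariate, stratification factor or interval method is named in the visible text, and redacted blocks follow directly.

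Section 11.2.8 addresses covariates: "Analysis of covariance will be performed to assess the effects of possible covariates on primary endpoint and some secondary endpoints as necessary". It names none in the visible text, and it too is followed by redacted text.

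Table 10.1-1 schedules two relevant measurements before randomisation: the row beginning "Pain Intensity (NRS", at the Baseline Visit, and the "End of Trial Assessment", during the implant procedures. Section 4.2 says of the temporary stimulation period: "The results of the screening trial can predict" the patient's outcome with the implanted system. Section 7.2 adds that "Subjects with a positive trial will proceed to receive permanent implant", and Section 10.7 defines success in that trial as "at least 50% pain reduction in their overall pain as compared with Baseline".

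Section 7 describes a "parallel group randomized controlled trial with an adaptive design"; the adaptive rules are not visible.

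**The concern.** Adjusting a randomised comparison for prognostic baseline variables usually narrows the interval. With a fixed margin of -0.20, a narrower interval means more power for the same number of subjects. Here the protocol itself points to a predictor, the screening-trial result, and schedules its collection, while the visible success rule makes no use of it. The only visible covariate plan is discretionary and separate from the success rule, which could leave the model and covariates to be chosen late.

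At stake would be efficiency only. Randomisation protects the unadjusted comparison, so neither the validity of the test nor the meaning of the margin is in question. The point would matter if the lost precision were appreciable and the plan clearly lacked adjustment. Both conditions need checking.

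**Working it through.** **1. Is adjustment shown to be absent?** Redacted blocks follow the success rule in 11.1.1.3 and the covariate sentence in 11.2.8. Text between 11.1.1.1 and 11.1.1.3, and after 11.2.2, is also redacted. Interval method, stratification, covariates and sample size could all stand there. Redacted text is not text missing from the plan, so absence can only be inferred. The visible part of 11.2.8 already covers the primary endpoint.

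**2. Inputs for the size of the gain.** From the documents: margin 0.20, two-sided 95% interval, 1:1 allocation, binary endpoint at 3 months. Sample size, responder rates and the prognostic strength of any covariate are not visible, so there is no figure of the plan to reproduce. Assumed here: 82 per arm and equal responder rates of 50%, 70% or 80%.

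**3. Unadjusted precision.** SE = sqrt(2p(1 - p)/n), and half-width = 1.96 × SE.
- p = 0.5: SE = sqrt(0.50/82) = 0.0781; half-width 0.153
- p = 0.7: SE = sqrt(0.42/82) = 0.0716; half-width 0.140
- p = 0.8: SE = sqrt(0.32/82) = 0.0625; half-width 0.122

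Power at a true difference of zero is Φ(0.20/SE - 1.96). For p = 0.7 this is Φ(2.794 - 1.96) = Φ(0.834), or 80%.

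**4. What adjustment does to the variance.** The adjusted estimator is the marginal risk difference, from standardised logistic regression or a linear model with robust SE. Simulation gives the ratio of adjusted to unadjusted variance. Trial relief is restricted to 50% or more, as Section 10.7 requires, and odds ratios for relief are per SD among all subjects trialled.
- Baseline NRS alone, odds ratio 1.0 to 1.3 per SD: 0.985 to 1.015
- NRS plus trial relief, relief odds ratio 1.0 to 1.65: 0.968 to 1.024
- NRS plus trial relief, relief odds ratio 2.7: 0.888 to 0.970

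**5. Translated to the interval and power.** Half-width is multiplied by the square root of the ratio r, and power becomes Φ(0.20/(SE × sqrt(r)) - 1.96). For p = 0.7 and 82 per arm:

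| Variance ratio r | sqrt(r) | Half-width | Power |
|---|---|---|---|
| 1.000 (unadjusted) | 1.000 | 0.140 | 79.8% |
| 0.985 | 0.992 | 0.139 | 80.4% |
| 1.015 | 1.007 | 0.141 | 79.2% |
| 0.968 | 0.984 | 0.138 | 81.1% |
| 1.024 | 1.012 | 0.142 | 78.9% |
| 0.970 | 0.985 | 0.138 | 81.0% |
| 0.888 | 0.942 | 0.132 | 84.3% |

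The ratios are ranges over several assumed settings, so the last row is an outer bound for 70% responders; direct simulation of a strong predictor there gave power of 83%.

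**6. Which row is realistic?** NRS is the covariate certain to be available as a number, yet no section calls it prognostic, and 11.1.1 scores the endpoint from the Percent Pain Relief questionnaire, which is not scheduled at baseline. For trial relief, Section 4.2 says that trial results predict outcome. It does not say that the degree of relief predicts outcome among those who passed. The entry rule cuts the spread: under the assumed distributions, the SD of relief among randomised subjects is 0.56 to 0.73 of that among all trialled. The content of the end-of-trial assessment is not visible, so a usable relief value cannot be taken for granted.

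**7. Is the unadjusted test sound?** At a true difference of -0.20, simulated false non-inferiority for the raw difference with a Wald interval is 2.3% to 2.9% against a nominal 2.5%. For the adjusted estimators it is 2.0% to 2.7%. The Wald interval is an assumption, because the plan's own method is not visible.

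**The case for a change.** The strongest contrary case is that adjustment costs only some wording and standard code, keeps the same estimand and margin, and would replace a discretionary covariate analysis with a fixed one. The protocol names a predictor itself. If that predictor were strong, power could rise from 80% to about 83%, while the worst loss found across the settings simulated is about 2.5% of variance.

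Part of this stands. Prespecified adjustment of a marginal risk difference would be a sound alternative, and the arithmetic behind the possible gain reproduces. What does not stand is the step from possible to expected gain. The favourable case requires an odds ratio of 2.7 per SD, which no passage supports. At weaker strengths the sign of the effect is uncertain. The worry about late choice of covariates concerns the supporting analysis in 11.2.8; the visible success rule does not depend on it.

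It is also unknown whether a change could still be made. Section 2 limits this protocol to subjects enrolled under Versions A to C, with new subjects under an Appendix A that is not visible, and the interim rules are not visible either. If an unblinded look has taken place, an adjusted interval could serve only as a sensitivity analysis, close to what 11.2.8 already foresees.

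**Conclusion.** The concern does not hold. The primary analysis is a valid ITT interval, lack of adjustment cannot be established from a redacted text, and covariate analysis of the primary endpoint is already foreseen. For Baseline NRS alone, the expected change in variance lies between 1.5% saved and 1.5% lost. With trial relief of up to moderate strength added, it lies between 3.2% saved and 2.4% lost, about one percentage point of power either way at 82 per arm and 70% responders. These sizes rest on assumed sample sizes, responder rates and prognostic strengths, since the documents show none. A much stronger predictor would give more, but nothing visible points to one. Adjusted and unadjusted analysis are both defensible here, and the plan's choice needs no correction.
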